## 1.4 Analysis Populations

_		

## 1.5 Clinical Event Committee and Data and Safety Monitoring Board

An independent Clinical Events Committee (CEC) has been established. The CEC is responsible for reviewing and classifying all serious adverse events, device- and/or procedure-related adverse events, and deaths.

CONFIDENTIAL Page 6 of 15

CRD 000 EFS

CL1010439 Statistical Analysis Plan Version A

An independent Data and Safety Monitoring Board (DSMB) has been established. The role of the DSMB is to monitor the overall conduct of the study, the rights, safety, and welfare of the study participants, and to evaluate interim data to determine if there are any specific safety concerns. The DSMB is responsible for communicating any safety or scientific concerns or perceived problems with the study to the sponsor as soon as possible. At the conclusion of each DSMB meeting, a recommendation will be made to the sponsor on whether to continue, suspend, modify, or stop the study.

#### 2. STATISTICAL PLAN AND METHODS

Sample size calculations were performed using the Power Analysis and Sample Size Software (PASS) (Version 14, NCSS Statistical Software). All statistical analyses will be performed using Statistical Analysis System (SAS) for Windows (version 9.4, SAS Institute Inc. Cary, NC).

## 2.1 Background Characteristics

Demographics and baseline characteristics, medical history, echocardiography core laboratory measures, procedural and device data, and treatment results will be summarized using descriptive summary statistics.

#### 2.1.1 Descriptive Statistics for Continuous Variables

For continuous variables (e.g., age, LVEF, LVEDV), results will be summarized with the numbers of observations, means, standard deviations, minimums, maximums, and 95% confidence intervals. Change from baseline, if applicable, may be included using these same descriptive statistics. Differences between subgroups, if applicable, will be summarized with differences of the two means, and 95% confidence intervals for the difference between the means.

#### 2.1.2 Descriptive Statistics for Categorical Variables

For categorical variables such as sex and NYHA classification, results will be summarized with subject counts and percentages/rates, and with exact 95% confidence intervals.

#### 2.1.3 Subject Disposition

The number and percentage of subjects screened, screen failure, enrolled, treated, and completed protocol-required follow-up visits will be summarized. Screen failure percentage is calculated from number of screened subjects and other percentages are calculated among number of enrolled or treated subjects. Subjects who discontinued from the study will be summarized by their primary

CONFIDENTIAL Page 7 of 15

reason for discontinuation.

#### 2.1.4 Protocol Deviation

The total number of protocol deviations and total number of subjects with deviations will be provided by deviation type. Number of protocol deviations by site will also be provided.

#### 2.2 Study Endpoint Analyses

## 2.2.1 Primary Safety Endpoint Analyses

The primary analysis will be based on the TP population. The composite endpoint will be summarized as the proportion of subjects with device success (definition in **Section 1.3.2.2**) and freedom from device- or procedure-related SAEs at 30 days post the index procedure, per CEC adjudication, along with the 95% exact confidence interval. Each component of the primary composite endpoint will also be summarized separately using descriptive statistics.

Similar analyses will be provided for the IPP population.

## 2.2.2 Primary Performance Endpoint Analyses

The primary performance endpoint is the proportion of subjects with mitral regurgitation (MR) grade ≤ 2, per echocardiography core laboratory, at 30 days post the index procedure. The trial is intended to demonstrate beneficial effects of the study device in reducing the MR severity in subjects treated with the Tendyne Mitral Valve System.

#### **Hypothesis**

The null and alternative hypotheses are:

 $H_0: P_D \leq P_{PG}$  $H_1: P_D > P_{PG}$ 

where  $P_D$  is the proportion of subjects with MR grade  $\leq 2$  at 30 days post the index procedure and  $P_{PG}$  is the performance goal. The performance goal is set at the 2.5% significance level.

CONFIDENTIAL Page 8 of 15

### Sample Size

### **Analysis**

The primary analysis will be based on the IPP population. The endpoint will be evaluated as a proportion of subjects with MR grade  $\leq 2$  at 30 days. If the 30-day core lab assessed echocardiography data is not available, the data from the next closest visit will be used. The hypothesis will be tested by comparing the one-sided 97.5% exact lower confidence bound of the observed 30-day MR grade  $\leq 2$  rate to the performance goal of . The null hypothesis will be rejected if this lower bound is greater than

Similar analyses will be provided for the TP population.

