14.1 Pre-Discharge

Pre-discharge data collection is to be done within 24 hours prior to discharge (or, in the event of prolonged hospitalization, within 10 days after the implant procedure). Pre-discharge requirements include clinical status, medications, an ECG, and documentation of any peri-operative AEs. It is recommended that serum creatinine be assessed at approximately 48 hours post implant.

An Implant card will be delivered to the patient when required by National regulation per specific Tendyne instructions for implant card distribution and completion, as applicable.

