14.2 Scheduled Follow-up Visits

Follow-up data must be documented using the appropriate eCRFs and image data must be submitted in electronic format.

Follow-up visits must occur at the following time points following implantation:

- Pre-discharge Within 24 hours prior to discharge or up to 10 days post-procedure, whichever occurs first
- One month 28 - 40 days
- Three months 90 ± 14 days
- Six months 180 ± 30 days
- One year 365 ± 45 days
- Two years 730 ± 60 days
- Annually thereafter until 5 years.

Subjects who have any part of the Tendyne Mitral Valve System introduced into the body but who do not end up with an implanted Tendyne Mitral Valve only need to be followed through one month or until resolution of any procedure or device related adverse event and then exited from the study. Subjects who are not exposed to the Tendyne Mitral Valve System will be exited from the study immediately. Documentation for subjects exited from the study must be completed using the appropriate CRF.

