14.4 Unscheduled Follow-Up Visits

If a subject presents for an unscheduled visit due to an AE that is serious (SAE) and/or device- or procedure-related, the following are required: clinical status; medication changes; and documentation of the AE using the appropriate eCRFs.

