14.6 Withdrawals

A subject may voluntarily withdraw from the study at any time. A subject may also be withdrawn from the study at the discretion of the investigator. In the event of withdrawal from the study, the investigator must ensure that the reason for the withdrawal is documented. If the subject had an AE, the subject must be followed until it is resolved, if possible, or until the investigator determines that the condition is stable. Withdrawn subjects will not be replaced.

All withdrawals must be reported to the sponsor using the appropriate eCRF.

15 Reinterventions and Explants

In the event that a subsequent procedure related to the Tendyne Mitral Valve is required at any time during a subject's study participation, the physician should obtain image data and otherwise attempt to characterize the valve *in situ*, to the extent feasible.

If an open-chest procedure is performed, then photographs should be taken. Photographs should be taken of the valve and/or native tissues before and after any modification or explant is done. The sponsor is particularly interested in understanding host response to the implanted valve (tissue ingrowth) and other device-host interfaces such as potential damage to native tissues including native leaflets, subvalvular structures and myocardium.

If a valve is explanted, the valve should immediately be placed in 10% neutral buffered formalin and returned to the sponsor for analysis. The valve must be handled carefully and as little as possible to prevent damage and preserve its integrity. The sponsor must be contacted for shipping and packaging materials and to arrange for transport.

All relevant data pertaining to the reintervention or explant must be documented on the appropriate eCRF. The physician should dictate an operative report and submit it to the sponsor along with any image data and photographs.

16 Heart Transplants or Subject Death

In the event of subject death or heart transplant, histological and engineering analyses of the *in situ* valve would provide valuable information. Therefore, a supplemental consent form may be used to authorize explant and donation of the heart to the sponsor. The sponsor must be contacted for shipping and packaging materials and to arrange for transport.

17 Data Management

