### 1.3 Study Design

This is a prospective, single-arm, multicenter study designed to evaluate the Tendyne Mitral Valve System in patients with significant mitral regurgitation.

This study is designed in accordance with the Mitral Valve Academic Research Consortium (MVARC) 2015 guidelines and the ISO 5840-3:2013 standard. The study is conducted under ISO 14155-2011 standard.

The data gathered in this study will be used to support conformity requirements for CE Mark of the Tendyne Mitral Valve System and to evaluate long-term safety and performance of Tendyne Mitral Valve in the intended population.

All enrolled subjects will be followed at 30 days, 90 days, 6 months, 12 months, and annually thereafter through 5 years from the index procedure.

A clinical investigation report will be prepared for CE Mark based on clinical data from at least 86 subjects who have completed or crossed the 12-month follow-up.

The study will continue to enroll after the CE Mark and collect long-term safety and performance data as part of the Tendyne post-market follow-up program.

CONFIDENTIAL Page 3 of 15

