#### 1.3.1.2 Primary Performance Endpoint

The primary performance endpoint is the proportion of subjects with mitral regurgitation (MR) grade ≤ 2, per echocardiography core laboratory, at 30 days post the index procedure. If the 30-day echocardiography data is not available, the data from the next closest visit will be used.

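### The rule for replacing a missing 30-day echo in the primary performance test states no direction, time limit or original-device condition, so a late or post-reintervention echo can count as a 30-day success

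*SAP*

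**What the plan says.** SAP 2.2.2 tests the proportion with MR grade ≤ 2 at 30 days in the IPP, using an exact one-sided 97.5% lower bound against a redacted goal. For a missing value it states: "If the 30-day core lab assessed echocardiography data is not available, the data from the next closest visit will be used". SAP 1.3.1.2 gives the same rule without naming the core lab in that sentence: "If the 30-day echocardiography data is not available, the data from the next closest visit will be used". Both sentences are complete, and neither points to a further condition.

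The visits that could supply a substitute are these:

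- SAP 1.3 lists the schedule as "All enrolled subjects will be followed at 30 days, 90 days, 6 months, 12 months" and then annually to 5 years. It lists no pre-discharge visit.
- Protocol 14.2 adds a pre-discharge visit ("Within 24 hours prior to discharge or up to 10 days post-procedure, whichever occurs first"), sets the one-month visit at days 28 to 40, and gives the following one as "Three months 90 ± 14 days".
- Protocol 14.1 names no echo at pre-discharge: "Pre-discharge requirements include clinical status, medications, an ECG, and documentation of any peri-operative AEs".
- Protocol 14.4 covers extra visits ("If a subject presents for an unscheduled visit due to an AE that is serious (SAE) and/or device- or procedure-related"). Its list of required items names no echo.
- Protocol section 15 says that when a later valve procedure is needed, "the physician should obtain image data and otherwise attempt to characterize the valve".

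Protocol 8.5.1 includes every subject with a completed implant. It does not require the subject to be alive or free of reintervention at day 30.

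**The concern.** In the readable text this is the only primary endpoint with a hypothesis test; the primary safety composite is estimated with a confidence interval. The substitution rule decides which grade enters that test for anyone without a 30-day echo.

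Three things are left open. The first is how far from day 30 the substitute may lie, and on which side. The second is whether an echo from an unscheduled visit or from a reintervention work-up counts as a visit. The third is whether the grade must describe the study valve as implanted. The third matters most. After an explant or a mitral reintervention, a low MR grade may reflect the second procedure, yet the rule would credit it to the study device at 30 days. In a report meant to support CE Mark, a choice of echo that the SAP does not fix is also open to the charge that it was made after the data were seen.

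**Working it through.** There is no plan figure to reproduce, because the goal, expected rate, sample size and power for this test are redacted. The check has two parts.

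**1. Which echo the rule selects (windows from protocol 14.2)**

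| Visit | Window (day) | Distance from day 30 |
|---|---|---|
| Pre-discharge | 10 at the latest | 20 to 30 days before |
| Three months | 90 − 14 = 76 to 90 + 14 = 104 | 46 to 74 days after |
| Six months | 180 − 30 = 150 to 180 + 30 = 210 | 120 to 180 days after |
| One year | 365 − 45 = 320 to 365 + 45 = 410 | 290 to 380 days after |

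On the SAP's own visit list, the substitute is the 90-day echo. If that is also missing, nothing readable stops the rule moving to six months, one year or later. The pre-discharge visit is nearer in days, but it can be selected only if a core-lab echo is taken there, and the readable text does not show one.

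A reintervention at any time before the substitute visit does not disqualify the echo. The conditions that the subject be alive, keep the original device and need no further procedure belong to device success (SAP 1.3.3.2). They are not part of the performance endpoint, which is MR grade alone.

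**2. How far a few subjects move the bound (illustration)**

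The counts are assumed. For n = 86 the scale is borrowed from the SAP 1.3 minimum for the CE Mark report; it is not the sample size of this test. The exact (Clopper-Pearson) one-sided 97.5% lower bound for x successes in n is the 0.025 quantile of Beta(x, n − x + 1).

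Start from 75/76, bound 92.9%. Suppose k of the 75 successes are echoes taken after a mitral reintervention or explant.

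| k | Coded as failure | Bound | Set to missing | Bound |
|---|---|---|---|---|
| 1 | 74/76 | 90.8% | 74/75 | 92.8% |
| 2 | 73/76 | 88.9% | 73/74 | 92.7% |
| 3 | 72/76 | 87.1% | 72/73 | 92.6% |

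Coding as failure lowers the bound by 2.1, 4.0 and 5.8 points (from 92.89% to 90.82%, 88.89% and 87.07%). Removing the values lowers it by at most about 0.3 points. With 86 subjects, 85/86 gives 93.7% and 83/86 gives 90.1%.

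The two right-hand columns explain the structure of the fix. Withdrawing the substitute hardly moves the main test, so the effect of these subjects shows only when they are counted as failures.

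**The case against.** The strongest reply is that this is a wording matter. The phrase is ordinary usage for the nearest other visit. On the SAP's own schedule, nearest and following both give the 90-day visit. A reader might infer that the two key words pull in opposite directions, so that analysts would routinely pick different echoes. That needs a pre-discharge echo, and protocol 14.1 names none. This part of the reply stands. What it does not supply is an upper limit in time, a ruling on unscheduled or reintervention images, or a device condition.

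A reader might also infer that subjects who die before day 30 are counted as successes through an early echo. The rule would permit it if such an echo were taken, but the readable text does not show that one is. The assessment table and most of the protocol's echocardiography section are missing from the available text, so the question cannot be settled either way.

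A third reply is that the reintervention gap lies in the endpoint rather than in the substitution rule: a day 28 to 40 echo after an earlier reintervention would also count. This is correct. Failing reintervened subjects only when their echo is a substitute would create a new inconsistency. It would also turn the deciding test into a composite measured against a goal whose derivation cannot be seen.

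Finally, these events are not hidden. Death, or a further procedure related to access or the device, fails device success and therefore the primary safety composite, and 30-day mortality has its own test. Redacted or unreadable text on analysis populations and missing data may also hold a relevant rule.

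**Conclusion.** The concern holds as a gap in the readable rule. Stated twice and without qualification, it lets a 90-day or much later MR grade stand for day 30, including one recorded after an explant or mitral reintervention. The plan should be amended, but the point does not undermine the trial.

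The practical reach is narrow. A subject must miss the day 28 to 40 echo, have a reintervention or explant, survive to a later echo and show grade ≤ 2. The effect on the decision cannot be computed. With the assumed counts, one to three such subjects are worth about 2 to 6 points on the lower bound, and the result would change only if the redacted goal lay between the paired bounds. The conclusion rests on the visible sentences; a condition elsewhere in the redacted text would reduce it to a missing cross-reference. The documents do not support saying that early deaths are in fact counted as successes.

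**What to change.** In SAP 1.3.1.2 and 2.2.2:

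- State one direction and a maximum day window for the substitute echo, and say whether unscheduled visits qualify.
- Allow a substitute only for a subject alive at day 30, with the original device in place and no mitral reintervention before the substitute echo. Otherwise the value is missing in the main test.
- Report the number of subjects substituted and the source visit of each.
- Keep the IPP test as primary. Add one prespecified sensitivity analysis that counts as failures all deaths, explants and mitral reinterventions before the 30-day assessment, whether the echo was on time or substituted. In the TP analysis already planned, count non-implantation as failure too.
- If redacted text already holds such a rule, cross-reference it from both places.

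Keeping deaths and reinterventions together in the sensitivity analysis treats them alike and leaves the deciding test as MR grade, which is prudent while the basis of the goal cannot be seen.

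The cost is SAP wording, one derived variable and one table. It needs no new data, since deaths and reinterventions are already recorded. The downside is that a few subjects lose a substitute value and the sensitivity proportion may be less favourable than the main one.

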## 2.2.3 Secondary Endpoint Analyses

#### 2.2.3.1 All-Cause Mortality at 30 Days

All-cause mortality at 30 days will be assessed to evaluate the acute safety of the Tendyne Mitral Valve System.

## **Hypothesis**

The null  $(H_0)$  and alternative  $(H_1)$  hypotheses are:

**H**0: P ≥

H1: P <

where P is the proportion of subjects who died within 30 days post the index procedure and 20% is the performance goal.

CONFIDENTIAL Page 9 of 15

#### **Analysis**

## 2.2.3.2 Change from Baseline in KCCQ at 6 Months and 12 Months

To evaluate the benefit of the Tendyne device, the Quality of Life as measured by the KCCQ scores at 6 and 12 months will be compared with those from baseline.

CONFIDENTIAL Page 10 of 15

# 2.2.3.3 Change from Baseline in Six-Minute Walk Test Distance at 6 Months and 12 Months

To evaluate the benefit of the Tendyne device, the distance walked at 6 months and 12 months as measured by the 6MWT will be compared with those from baseline.

Descriptive statistics will be provided for change from baseline in distance walked on the 6MWT at each follow-up visit. Proportion of subjects with improvement of clinically important differences of at least 24 meters and at least 50 meters (a component of Individual Patient Success, see **Section 1.3.3.3**) at follow-up visit from baseline will also be provided.

#### 2.2.4.4 Change in Proportion of NYHA Functional Class I or II at 12 Months

The proportion of subjects with NYHA Functional Classification I or II at 12 months will be evaluated at one-sided 5% level of significance using the McNemar's test. The primary analysis will be based on the IPP population.

The null and alternative hypotheses are stated as:

 $H_0$ :  $P_{M12}$ ,  $NYHA I/II \le P_B$ , NYHA I/II vs.

 $H_1$ :  $P_{M12, NYHA I/II} > P_{B, NYHA I/II}$ 

where  $P_{M12, NYHA I/II}$  and  $P_{B, NYHA I/II}$  represent the proportion of NYHA Classification I or II at 12 months and baseline, respectively.

Descriptive statistics will be provided for NYHA Functional Classification at baseline each follow-up visit.

CONFIDENTIAL Page 11 of 15

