2.1 Executive Summary

The purpose of this expanded clinical study is to evaluate the performance and safety of the Tendyne Mitral Valve System in the treatment of severe mitral regurgitation in patients with functional disability greater than or equal to NYHA Class II, who are not suitable candidates for surgical replacement with otherwise available devices. The data gathered in this study will be used to support conformity requirements for CE Mark of the Tendyne Mitral Valve System, using an appropriately powered sample size to enable assessment of the study safety and performance endpoints of the Tendyne Mitral Valve System in the intended populations.

This study will be continued after the CE Mark to collect long-term safety and performance data as part of the Tendyne Mitral Valve System post-market follow-up program. All patients shall continue to be followed through 5 years in the post-market setting.

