8.4 Handling Study Discontinuations

Study drop-outs will be listed along with the reason for termination per Section 8.1 of the protocol. Drop-outs will be censored from the analysis with no data imputation. Deviations from the protocol will also be summarized by deviation type as well as total. The primary statistical analysis will be based on subject counts. A subject with more than one deviation will be counted only once toward the rate based on the total number of subjects with protocol deviations.

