#### 1.3.3.2 Device Success

Device success is a composite endpoint measured at 30 days post the index procedure and all post-procedural time points, defined as subject is alive with the following:

- Disabling stroke free, and
- Original intended device in place, and
- · No additional surgical or interventional procedures related to access or the device, and
- Intended performance of the device:

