#### 1.3.3.3 Individual Patient Success

Individual patient success is a composite endpoint measured at 1 year post the index procedure, defined as device success (**Section 1.3.2.2**) and all of the following:

- No re-hospitalizations or re-interventions for heart failure
- Improvement in New York Heart Association (NYHA) functional class (≥ 1 compared to baseline)

CONFIDENTIAL Page 5 of 15

- Improvement in distance walked, 6 Minute Walk Test (6MWT) (≥ 50 meters compared to baseline)
- Improvement in Kansas City Cardiomyopathy Questionnaire scores (KCCQ) (≥ 10 compared to baseline)

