#### 2.2.4.3 Individual Patient Success

The primary analysis will be based on the IPP population. The composite endpoint will be summarized as the proportion of subjects with individual patient success at 1 year (see definition in **Section 1.3.2.3**). The count and proportion of subjects that meet the criteria of individual patient success will be summarized along with the 95% exact confidence interval. The individual components of the composite endpoint will also be provided.

Similar analyses will be provided for the TP population.

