#### 2.5 Handling of Missing Data

**Multiplicity Issues** 

2.6

Analyses will consist of all available data as the full analysis set. Data will only be absent from analyses of study outcomes in the event that they were not available for collection.

In general, missing values in any of the endpoints will not be imputed when summarizing these endpoints using descriptive statistics. All available data collected will be used in the summaries.

CONFIDENTIAL Page 13 of 15

CL 1010439 Statistical Analysis Plan Version A

CONFIDENTIAL Page 14 of 15

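### On the readable text, the 12-month NYHA test in SAP 2.2.4.4 describes only implanted subjects alive with a 12-month class; it should be labelled so and reported beside an analysis of the full IPP that counts deaths

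*SAP*

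**What the plan says.** - **The test.** SAP 2.2.4.4: "The proportion of subjects with NYHA Functional Classification I or II at 12 months will be evaluated at one-sided 5% level of significance", using McNemar's test, with the IPP as the primary analysis population. The alternative is that the class I/II proportion is higher at 12 months than at baseline. The section reads through without a visible gap. It gives no denominator for the 12-month proportion, no estimand and no rule for deaths, and does not say whether the test is exact or asymptotic.
- **Missing data.** SAP 2.5 uses all available data: "Data will only be absent from analyses of study outcomes in the event that they were not available for collection". Its readable no-imputation sentence is limited to descriptive summaries. Protocol 8.4: "Drop-outs will be censored from the analysis with no data imputation". It does not say whether a death is a drop-out.
- **The neighbouring 1-year endpoint.** SAP 1.3.3.3: "Individual patient success is a composite endpoint measured at 1 year post the index procedure, defined as device success" plus functional criteria. Device success applies at 30 days and "all post-procedural time points, defined as subject is alive with the following" (SAP 1.3.3.2). In SAP 2.2.4.3, whose primary population is also the IPP, "The composite endpoint will be summarized as the proportion of subjects with individual patient success at 1 year", with a confidence interval and no test.
- **Who is counted.** The CE Mark report draws on "at least 86 subjects who have completed or crossed the 12-month follow-up" (SAP 1.3). The study treats severe regurgitation "in patients with functional disability greater than or equal to NYHA Class II" (Protocol 2.1), so a baseline class of I or II normally means class II.
- **Not readable.** The IPP definition (SAP 1.4), the rest of SAP 2.5 and Protocol 23.10.

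**The concern.** A subject who dies before the 12-month visit has no 12-month class and cannot form a McNemar pair. Unless a rule assigns an outcome, the pairs are implanted subjects who are alive and were classified at 12 months. A subject in class II at baseline who dies is one fewer implanted subject in class I/II, and the test does not register that loss. Deaths in class III/IV do not matter here, because those subjects are outside I/II at both times.

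The plan names the IPP as the population, and its other 1-year functional endpoint counts death as failure. A reader of the CE Mark report could therefore take a significant result to mean that more implanted patients are in class I/II at one year. The test does not establish that. The reported 12-month percentage would also have a smaller denominator than the population named beside it.

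**Working it through.** The documents give no readable sample size, power or expected rate for this test, so there is no stated figure to reproduce.

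**1. Notation.** Let b = subjects moving from III/IV to I/II, c = class II survivors moving to III/IV, d = deaths among baseline class II. The survivors-only exact one-sided test is p = P(X ≥ b), X ~ Binomial(b + c, 0.5). The share of implanted subjects alive in I/II changes by (b − c − d)/N. Counting death as not I/II replaces c by c + d.

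**2. Example of the mechanism, N = 86.** There are 34 subjects in class II (5 die, 29 stay) and 52 in class III/IV (10 die, 5 improve).
- All implanted: 34/86 at baseline, 29 + 5 = 34/86 at 12 months. No change.
- Survivors only: 29/71 (41%) to 34/71 (48%); 5 against 0, p = 0.5^5 = 0.031.
- Deaths counted: 5 against 5, P(X ≥ 5 | 10) = 0.62.

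Some worsening does not remove the effect: b = 7, c = 1, d = 6 gives p = 0.035 survivors-only and 0.60 with deaths counted.

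**3. How often.** Assumptions, none given for this trial: class II share s; 12-month mortality m, equal across classes; r = 75% of class II survivors remain in I/II; exact test at 5%; N = 86 (the SAP 1.3 minimum). The upper mortality values, 14.3% and 17.6%, are borrowed from the surgical trial in severe ischemic MR cited in Protocol 2.4.2.3. The condition is no change in the share alive in I/II:
- P(improve) = s − s(1 − m)r
- P(worsen, alive) = s(1 − m)(1 − r)
- P(class II death) = s·m

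The difference between the first two is exactly s·m. With s = 0.40 and m = 0.176 they are 0.1528, 0.0824 and 0.0704, and 0.0824 + 0.0704 = 0.1528. Summing exact rejection probabilities over all outcomes gives, for the survivors-only test:

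| Class II share | m = 5% | 10% | 14.3% | 17.6% |
|---|---|---|---|---|
| 10% | 0.018 | 0.030 | 0.044 | 0.057 |
| 20% | 0.041 | 0.073 | 0.112 | 0.149 |
| 30% | 0.060 | 0.112 | 0.176 | 0.237 |
| 40% | 0.073 | 0.143 | 0.229 | 0.310 |

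With deaths counted, every cell lies between 0.012 and 0.034.

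**4. Sensitivity.**
- Only class II mortality drives it: 5% in class II with 25% in III/IV gives 0.060-0.073 at shares 30-40%.
- Retention 65-90%, shares 30-40%, mortality 14.3-17.6%: 0.156-0.443.
- If 10% of living subjects also lack a 12-month class at random, the 0.176-0.310 block becomes 0.158-0.282.

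**5. When there is a real gain.**
- Large gain (80% of survivors in I/II, m = 17.6%, shares 30-40%, retention 75-90%): the test with deaths counted still rejects in at least 93%. The share of implanted subjects is 0.80 × 0.824 = 0.66.
- True 10-point rise in the share alive in I/II (shares 20-40%, mortality 10-17.6%, retention 75%): rejection is 70-85% survivors-only and 37-55% with deaths counted.

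**The case against.** The strongest reply is that nothing readable says deaths are excluded. SAP 2.5 limits its no-imputation sentence to descriptive summaries, Protocol 8.4 speaks of drop-outs, and the places where a death rule would sit cannot be read. This stands: exclusion is inferred from the need for pairs and the available-data wording. A reader might infer that the plan removes deaths by rule, or that its hypotheses contradict its test. The documents support neither, since the hypotheses name no denominator.

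A second reply is that the test is correct for what it measures. This also stands. Deaths enter neither discordant cell and cannot by themselves produce significance; the exact test needs at least 5 improvers. In the 30-40% share cells at 14.3-17.6% mortality, the survivor share really rises, from 30% to 35-36% or from 40% to 47-49%. These are false rejections only if the target is all implanted subjects, which the SAP does not state.

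Third, deaths are visible elsewhere: device success and its components are reported at follow-up visits (SAP 2.2.4.2), and individual patient success counts death. That helps, but neither endpoint carries a test, and neither tells a reader what this p-value refers to.

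Fourth, every input is assumed, and the step 2 example has no worsening among class II survivors, which would be very unlikely at 75% retention. It shows the mechanism, not a frequency.

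**Conclusion.** The point holds for the readable text at low to moderate severity. The McNemar test answers a question about implanted subjects alive with a 12-month class, and the SAP does not say so. Read as a gain among all implanted subjects, it can be significant with no such gain. Under the step 3 assumptions this happens in 2-15% of trials at class II shares of 10-20% and in 6-31% at 30-40%, against 1-3% with deaths counted. At low class II mortality or a small class II share the effect is negligible. With a large gain the decision rarely changes and the issue is the reported share, for example 80% against 66%.

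A reader might go further and call the test invalid, or ask that a death composite replace it. The documents do not support the first, because a survivor comparison is legitimate if labelled. The second is a debatable trade-off, given the loss of power, and is not needed to correct the reading. A death rule in the unreadable text would reduce the point to a missing cross-reference.

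**What to change.** In SAP 2.2.4.4:
1. Label the McNemar result as applying to implanted subjects alive with a 12-month NYHA class.
2. Pre-specify beside it an analysis in the full IPP with death before the 12-month visit counted as not NYHA I/II, consistent with individual patient success.
3. Report the number of deaths by baseline class and the number of living subjects without a 12-month class.
4. Base any claim about all implanted subjects on the deaths-counted analysis.

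If unreadable text already holds a death rule, cite it in 2.2.4.4 instead.

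The cost is a few sentences and one derived value. No new data are needed: deaths go to the CEC (SAP 1.5), and NYHA class is collected at baseline and each scheduled visit (Protocol 12.6). The downside is a less favourable second figure and lower power for any claim about all implanted subjects. The survivor test keeps its own power.
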